### **Progression free survival (PFS)**

PFS is defined as the time (in months) from the date of first study medication to the earliest date of disease progression or death due to any reason whichever occurs first.

HMPL-523

PFS (months) = ([date of progression or death or censoring] - [date of first dose of study medication] + 1)/30.4375.

A patient is deemed to be censored according to the rules specified in **Error! Reference source not found.** below.

Error! Reference source not found.: **Progression-Free Survival Censoring Rules**

#	Situation	Date of Progression or Censoring	Outcome	Event/Censor reason
1	Death (without previously documented progressive disease [PD]) within two evaluable tumor assessments [a] from last evaluable tumor assessment or first dose (if no post-baseline tumor assessment)	Date of death	Event	Death
2	Death (without previously documented PD) after two or more consecutive missed/non-evaluable tumor assessments [a] from last evaluable tumor assessment or first dose (if no post-baseline tumor assessment)	Date of last evaluable tumor assessment or date of first dose (if no post-baseline tumor assessment)	Censored	Death after two or more consecutive missed or NE tumor assessments
3	Progression within two evaluable tumor assessments [a] from last evaluable tumor assessment or first dose (if no post-baseline tumor assessment before PD)	Date of progression	Event	Disease Progression
4	Progression after two or more consecutive missed/non-evaluable tumor assessments [a] from last evaluable tumor assessment or first dose (if no post-baseline tumor assessment before PD)	Date of last evaluable tumor assessment or date of first dose (if no post-baseline tumor assessment before PD)	Censored	Progression after two or more consecutive missed or NE tumor assessments
5	Progression after new anti-cancer treatment	Date of last evaluable tumor assessment before new anti-cancer treatment or date of first dose (if no post-baseline tumor assessment before new anti-cancer)	Censored	Progression after new anti-cancer therapy
6	No baseline tumor evaluable assessment and alive	Date of first dose	Censored	No baseline assessment
7	No post-baseline tumor evaluable assessment and alive	Date of first dose	Censored	No post-baseline assessment

HMPL-523

8	New anti-cancer treatment started with no progression [b] /death	Date of last evaluable tumor assessment before new anti-cancer treatment or date of first dose (if no post-baseline tumor assessment before new anti-cancer)	Censored	Initiation of new anti-cancer therapy without PD/death observed
9	No disease progression or death	Date of last evaluable tumor assessment or date of first dose (if no post-baseline tumor assessment)	Censored	Progression free at time of analysis: the patient is known to be alive without any progression happened at the end of study date

[a] time period that identifies two consecutive missed/non-evaluable tumor assessments is calculated as 2\*(the planned duration between assessments + protocol allowed visit window) from the last evaluable tumor assessment or date of first dose (if no post-baseline evaluable tumor assessment). According to protocol, tumor assessment will be conducted every 8 weeks for the first 24 weeks and every 12 weeks thereafter ( $\pm 7$  days). Additional details are provided below.

[b] See algorithm below

Given the schedule of visit assessments, the definition of two missed consecutive tumor assessment visit may vary; please refer to following rules:

- If the last evaluable tumor assessment before PD/death is less than 120 days (week 16 which is 8 weeks before week 25, and allowing for 7 days for late visit, hence  $7*16$  weeks + 7 days for a late visit + 1 day\*=120 days) then two consecutive assessments equates to 126 days since last evaluable tumor assessment, allowing for early and late visits ( $2*8$  weeks + 7 days for an early assessment + 7 days for a late assessment).

\*Note the 1 day comes from study days = date of tumor assessment – date of first dose + 1 day.

- If the two missed assessments occur over the period when the scheduled frequency of tumor assessments change from 8-weekly to 12-weekly, which means last evaluable tumor assessment is from week 16 to 25 (days 120 to 176), then two consecutive assessments equates to 154 days ( $7*8$  weeks +  $7*12$  weeks + 7 days for an early assessment + 7 days for a late assessment).
- From day 176 (week 25) onwards (when the scheduling changes to 12-weekly assessments), two missing consecutive assessments equates to 182 days ( $2*12$  weeks + 7 days for an early assessment + 7 days for a late assessment).

[b] for patients who receive new anti-cancer therapy, the following rules will apply:

- If the start date of new anti-cancer therapy is completely missing, then impute the date as

HMPL-523

last dose of study treatment + 1.

- If the start date of new anti-cancer therapy is partial, the imputation rules refer to [section 7.9](#).
- If new anti-cancer therapy is started without PD or is started prior to PD or death, the PFS will be censored at the date of the last evaluable tumor assessment no later than the date of initiation of new anti-cancer therapy (i.e. if an assessment occurs on the same day as the start of new anti-cancer therapy, the assessment will be used as it will be assumed the assessment occurred prior to the administration of new anti-cancer therapy).
- If a patient has only a baseline visit or does not have an assessment that is no later than the date of initiation of new anti-cancer therapy, the PFS will be censored at the date of first dose.

The median and quartiles for PFS and the PFS rates at 6 months, 12 months, together with their two-sided 95% confidence intervals will be estimated for each dose level (Stage 1) and malignancy type (Stage2) using the Kaplan-Meier method. The 95% CI for the median will be calculated from a log-log transformation based on the method by Brookmeyer and Crowley ([Brookmeyer, R., & Crowley, J. 1982](#)). Kaplan-Meier curves will be plotted.

Frequency and percentage for each type of event (PD or death) and censoring reasons will be presented as categories.

The PFS time or censoring time and the reasons for censoring will also be presented in a patient listing.

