5.6.12 Tumor and Response Evaluation

All evaluable lesions should be assessed and documented at screening and re-assessed at each subsequent tumor evaluation, using blood test, physical examination, and contrast-enhanced CT scans (neck, chest, abdomen, and pelvis) for indolent NHL and/or positron emission tomography (PET)-CT for HL and aggressive NHL. Enhanced magnetic resonance imaging (MRI) may be used instead of enhanced CT scans in patients for whom CT scans are contraindicated.

Tumor assessment will be conducted every 8 weeks (± 7 days) for the first 24 weeks and every 12 weeks (± 7 days) thereafter until the patient has the first progression, starts new anticancer therapy, or dies. Patients who discontinue study drug due to reasons other than disease progression will remain on the study and will be followed quarterly for tumor assessment until the patient has their first progression, starts new anticancer therapy, or dies or until 12 months after their initial dose of the study drug. Tumor assessment will also be conducted at study completion or early termination (for reasons other than disease progression).

The same imaging procedure and laboratory tests used to define evaluable lesions at baseline should be used throughout the study for each patient.

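### The SAP's two-missed-scan limits for PFS ignore the quarterly off-drug schedule, so one missed scan can wrongly censor the event of a patient who stopped drug early

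*SAP*

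**What the plan says.** Rows 2 and 4 of the PFS censoring table in SAP Section 16.1.1 censor a death or progression that comes after two or more consecutive missed or non-evaluable assessments. The censoring date is the last evaluable scan, or first dose if there is none. Note [a] defines the test: the "time period that identifies two consecutive missed/non-evaluable tumor assessments is calculated as" twice the sum of two terms, "the planned duration between assessments + protocol allowed visit window) from the last evaluable tumor assessment or date of first dose". The interval comes from one schedule only: "tumor assessment will be conducted every 8 weeks for the first 24 weeks and every 12 weeks thereafter", with a 7-day window. Three limits follow, chosen by the study day of the last evaluable scan:

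- before Day 120, "then two consecutive assessments equates to 126 days since last evaluable tumor assessment";
- Day 120 to 176, "then two consecutive assessments equates to 154 days";
- from Day 176, "two missing consecutive assessments equates to 182 days".

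No limit depends on whether the patient is still on drug.

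Protocol Section 5.6.12 sets a second schedule: "Patients who discontinue study drug due to reasons other than disease progression will remain on the study and will be followed quarterly for tumor assessment". This runs until progression, new anticancer therapy, death or 12 months after first dose. Section 5.7.1 agrees. The Schedule of Activities (Protocol Appendix 1) counts these visits from the end of treatment with a 7-day window. A scan is also required at the early termination visit, 30 ± 7 days after the last dose. The SAP carries the same quarterly follow-up in its visit-window table (Section 7.6, marked for CT/PET-CT) and in footnote 3 of its Appendix 1.

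**The concern.** A limit meant to detect two missed scans must match the spacing of the scans that were due. A patient who stops drug early without progression goes straight to scans about 12 or 13 weeks apart, yet is judged against 8-week spacing, or a mix of 8 and 12 weeks, until about Day 176. One missed quarterly scan can then use up the whole allowance, and an observed event is discarded on the stated ground that two or more assessments were missed.

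The patients at risk have left treatment early, often for reasons that may relate to prognosis, so the censoring may be informative. Preliminary efficacy in Stage 2 is a primary objective. The SAP plans PFS medians and 6- and 12-month rates by malignancy, in cohorts that Protocol Table 2 puts at 25 (HL), 9 (PTCL), 7 (CLL post-BTK) or fewer.

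**Working it through.** **Inputs.** On-treatment intervals 56 and 84 days, window 7 days (SAP note [a]). Off-drug scans quarterly from end of treatment, window 7 days (Protocol Appendix 1). Termination scan at 30 ± 7 days after last dose (Protocol 5.6.12 and 5.7.1). The documents do not give a quarter in days; I take q = 84 and q = 91 as the range. An event is treated as censored when its gap from the last evaluable scan is greater than the limit.

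**1. The SAP's own figures.** 2 × (56 + 7) = 126; 56 + 84 + 7 + 7 = 154; 2 × (84 + 7) = 182. Cut-offs: 7 × 16 + 7 + 1 = 120 and 7 × 24 + 7 + 1 = 176. All reproduce.

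**2. The same formula on the quarterly schedule.** 2 × (84 + 7) = 182 days, or 2 × (91 + 7) = 196 days. Against 126 the shortfall is 56 to 70 days; against 154 it is 28 to 42 days; against 182 it is 0 to 14 days.

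**3. Gap containing exactly one missed quarterly scan, with progression found at the next.** From a quarterly scan the gap is 2q ± 14; from the termination scan it is 2q − 30 ± 14.

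| Last evaluable scan | q | Gap, nominal (range) | Limit 126 | Limit 154 | Limit 182 |
|---|---|---|---|---|---|
| Quarterly | 84 | 168 (154–182) | censored | censored, unless exactly 154 | event |
| Quarterly | 91 | 182 (168–196) | censored | censored | event; censored if 183–196 |
| Termination | 84 | 138 (124–152) | censored, unless 124–126 | event | event |
| Termination | 91 | 152 (138–166) | censored | event; censored if 155–166 | event |

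With no missed scan the largest gap is q + 14 = 98 to 105 days, so nothing is wrongly censored then.

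**4. Worked cases (q = 91).**
- Drug stopped Day 57, termination scan Day 87, Day 148 scan missed, progression Day 239. Gap 239 − 87 = 152 > 126: censored at Day 87 with one scan missed. With q = 84 the scans fall on Days 141 and 225; the gap is 138, still censored.
- Same patient, death instead. The limit runs out on Day 87 + 126 = 213. A death on Day 214 to 238 is censored before the second quarterly scan is due.
- Same patient, Day 148 scan evaluable (limit now 154), Day 239 missed, progression Day 330. Gap 182 > 154: censored at Day 148.
- Contrast: drug stopped Day 100, last scan Day 191, Day 282 missed. The limit is 182, so an event up to Day 373 counts.

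**5. Who is exposed, at nominal timing.** A termination scan before Day 120 means last dose by Day 119 − 30 = 89. A first quarterly scan by Day 175 means last dose by Day 175 − 91 = 84 or 175 − 84 = 91. So these are patients off drug by about Day 90, without progression or new anticancer therapy, who then miss a scan and have an event beyond the limit.

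**The case against.** **Is there really a second schedule?** The first sentence of the relevant paragraph in Protocol 5.6.12 runs the 8/12-week scans to progression without mentioning treatment status, so one could say that schedule applies to everyone. The next sentence treats patients off drug separately, Appendix 1 anchors their scans at end of treatment, and the Amendment 5 summary presents this as a clarification of imaging for those patients. This objection fails.

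**Scope.** A reader might infer that any progression or death after one missed quarterly scan is censored. The table rules that out. From Day 176 a single miss at nominal timing stays an event. In the 154-day bracket a gap starting at the termination scan normally does too. A death inside the limit is always an event (row 1). This objection stands and sets the bounds of the point.

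**Direction.** A reader might infer that PFS is raised throughout. It is not. As an illustration with assumed numbers, take 15 at risk, five other events before the removed one, and no other censoring. Before the removed event, survival is 10/15 = 0.667 with the patient kept and 9/14 = 0.643 with the patient censored early, so the curve is too low. Once the removed event is counted, the comparison is 9/15 = 0.600 against 0.643, so the curve is too high from there on. This objection stands too.

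**Importance.** PFS here is descriptive, in a Phase I study closed to enrollment, and the SAP tabulates and lists censoring reasons, so affected patients can be found. That limits the harm, but the listed reason would itself be wrong.

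**Conclusion.** The point holds for PFS in a defined region: last evaluable scan before Day 120, or on Day 120 to 175 and a full quarter before the missed scan. There, the rule for two or more missed assessments is normally triggered by one. Relative to the SAP's own formula from a quarterly scan, the limits are 56 to 70 and 28 to 42 days short. This rests on a quarter of 84 to 91 days and on visits near their nominal dates.

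The effect on the estimates cannot be sized, because the documents do not say how many patients stopped early without progression and then missed a scan. One patient is 1/25 = 4% of the HL cohort, but that is a share of patients, not a change in a Kaplan-Meier estimate.

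A reader might also infer that DoR is distorted in the same way. The documents do not establish this. The DoR paragraph refers to the PFS rules only for patients without progression or death, whereas rows 2 and 4 concern patients who had one. Whether those rows apply to DoR is unclear, and the SAP should say.

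This is a cheap correction worth making before database lock, not a threat to the study's conclusions.

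**What to change.** Add an off-drug branch to note [a] in SAP Section 16.1.1:

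- State the number of days taken as a quarter for analysis.
- For a patient off HMPL-523 without progression whose last evaluable scan is at or after end of treatment, count missed assessments against the quarterly schedule. From a quarterly scan the limit is 2 × (q + 7), i.e. 182 days (q = 84) or 196 days (q = 91). From the termination scan it is 2q − 30 + 14, i.e. about 152 or 166 days.
- If the last evaluable scan was on treatment, count the assessments actually scheduled (on-treatment, termination, quarterly) and do not use the longer limit. Example: scan Day 57, Day 113 scan missed, drug stopped Day 120, Day 150 termination scan missed, progression at the Day 211 quarterly scan. Two assessments were missed and the gap is 154 days. The present 126-day limit censors this as intended; a flat 196 days would wrongly count it as an event.
- State whether rows 2 and 4 apply to DoR and, if so, use the same limits.

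Cost: a short paragraph and a conditional step in the program. Treatment end dates and scan dates are already among the data the SAP uses, and SAP Section 2 allows revision before the final database lock.

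### The PFS two-missed-scan limits switch at the late edge of the Week 16 and Week 24 windows, so events after only one missed scan are censored

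*SAP*

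**What the plan says.** Rows 2 and 4 of the PFS censoring table (SAP 16.1.1, Progression free survival) censor death or progression at the last evaluable scan when two or more consecutive assessments were missed or not evaluable. For progression, the reported reason is "Progression after two or more consecutive missed or NE tumor assessments".

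Footnote [a] turns this into a time limit of twice "the planned duration between assessments + protocol allowed visit window". Three bullets then set the limit by the study day of the last evaluable scan:

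- 126 days: "If the last evaluable tumor assessment before PD/death is less than 120 days". Day 120 is derived from "week 16 which is 8 weeks before week 25, and allowing for 7 days for late visit".
- 154 days: "If the two missed assessments occur over the period when the scheduled frequency of tumor assessments change from 8-weekly to 12-weekly". The SAP then translates this condition into a bracket of study days: "which means last evaluable tumor assessment is from week 16 to 25 (days 120 to 176), then two consecutive assessments equates to 154 days".
- 182 days: "From day 176 (week 25) onwards".

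Scans are 8-weekly to Week 24 and 12-weekly after that, each with a 7-day tolerance either way (Protocol 5.6.12; SAP 16). The SAP will report "The median and quartiles for PFS and the PFS rates at 6 months, 12 months", by dose level in Stage 1 and by malignancy type in Stage 2.

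**The concern.** The limit should follow from the next two scheduled scans. After Week 16 these are Weeks 24 and 36, one 8-week and one 12-week interval. After Week 24 they are Weeks 36 and 48, two 12-week intervals. Because the brackets change only on the last allowed day of the Week 16 and Week 24 windows, nearly every patient whose last scan was at one of those visits gets the limit meant for the visit before. A patient who missed one scan is then treated as having missed two. A real event becomes a censored time, with a wrong reason attached.

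All the affected events fall before 12 months. Removing them raises the 12-month PFS rate. The same patients also leave the risk set at Week 16 or Week 24 although they were event-free beyond six months, which lowers the 6-month rate. Preliminary efficacy in the expansion stage is a primary objective of the trial.

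**Working it through.** **Inputs.** Study day = date minus first-dose date + 1 (SAP note under the bullets), so the nominal scan day is 7 × week + 1 and each window is ±7 days.

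| Scan | Nominal day | Window |
|---|---|---|
| Week 8 | 57 | 50-64 |
| Week 16 | 113 | 106-120 |
| Week 24 | 169 | 162-176 |
| Week 36 | 253 | 246-260 |
| Week 48 | 337 | 330-344 |

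**The SAP's own figures reproduce.** Limits: 2 × (56 + 7) = 126; 56 + 84 + 7 + 7 = 154; 2 × (84 + 7) = 182. Cut-points: 7 × 16 + 7 + 1 = 120 and 7 × 24 + 7 + 1 = 176. Both cut-points are late window edges.

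**On-time examples, one scan missed.**

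- Week 16 done, Week 24 missed, progression at Week 36: gap 253 − 113 = 140. The limit applied is 126, so the event is censored.
- Week 24 done, Week 36 missed, progression at Week 48: gap 337 − 169 = 168. The limit applied is 154, so the event is censored.

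**When the limit runs out.**

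- Last scan on days 106-119, plus 126, ends on days 232-245. The Week 36 window opens on day 246.
- Last scan on days 162-175, plus 154, ends on days 316-329. The Week 48 window opens on day 330.

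In every affected case the limit ends before the second scan is due, so two scans cannot yet have been missed.

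**All in-window timings.** Each pair of visits gives 15 × 15 = 225 combinations of last-scan day and next-attended-scan day, with exactly one scan missed between them.

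| Last scan to progression | Gap (days) | Censored under SAP | Censored with cut-points 106 and 162 |
|---|---|---|---|
| Week 8 to 24 | 98-126 | 0 of 225 | 0 |
| Week 16 to 36 | 126-154 | 210 of 225 | 0 |
| Week 24 to 48 | 154-182 | 210 of 225 (224 if day 176 gets 154 days) | 0 |
| Week 36 to 60 | 154-182 | 0 of 225 | 0 |

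Day 176 belongs to both the second and the third bullet, hence the two counts. When two scans are missed and progression is found at the next attended one, both sets of cut-points censor every timing.

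**Affected events.** After a Week 16 scan on days 106-119 the wrongly censored gaps are 127-154 days, which are event days 233-260 (÷ 30.4375 = 7.7-8.5 months). After a Week 24 scan on days 162-175 they are 155-182 days, event days 317-344 (10.4-11.3 months). For an on-time scan the one-missed range stops when the second window closes: 260 − 113 = 147 days and 344 − 169 = 175 days.

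**Size.** The documents give no missed-scan rate, so it was assumed. The simulation also assumed exponential PFS with medians of 4, 8 and 11 months, 15% of events being deaths, 24 months of follow-up, the on-treatment schedule (scans on the nominal day or uniform within ±7 days), and no censoring for new therapy.

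| Scans missed | Events wrongly censored | Rise in 12-month rate (points) |
|---|---|---|
| 5% | 1.9-2.3% | 0.5-1.1 |
| 10% | 3.5-4.1% | 1.1-2.1 |
| 20% | 5.8-6.8% | 2.0-3.7 |

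The 6-month rate falls by 0.1-1.8 points. If every patient had an event, 1.9-6.8% is about 1-3 of the 48 expansion patients and 0.5-1.7 of the 25 HL patients (Protocol 4.5, Table 2).

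**The case against.** The strongest reply is that the effect is small and the text is ambiguous rather than simply wrong.

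- **Ambiguity.** The second bullet's week label starts at Week 16, which would give an on-time Week 16 scan 154 days. Only the day numbers exclude it. This is true, but the first bullet spells out the day number and its derivation, and a programmer will most likely code the days.
- **Footnote [a].** It is a one-interval formula and does not say what to do when the interval changes, so it cannot be held against the 126 days after Week 16. That stands. For a Week 24 scan, however, both following intervals are 12 weeks and the formula gives 2 × (84 + 7) = 182, against 154 applied. After Week 16 the conflict is with rows 2 and 4 of the table and with the second bullet's own description.
- **Size depends on the assumed median.** Study 2015-523-00CH1 shows median PFS from 1.9 to 14.9 months across its expansion cohorts (Protocol 2.2.4.4), and the documents give no PFS figure for HL or PTCL, which make up 34 of the 48 patients. With a 2-month median, scans on the nominal day and 5-20% missed, the 12-month rate rises by only 0.1-0.4 points and the 6-month rate falls by 0.7-2.2. In fast-progressing disease the 6-month effect is therefore the larger one.
- **Low stakes.** PFS is descriptive, no decision rule uses it, and sampling error is far larger: an exact 95% interval for 10 of 25 runs from 21% to 61%. The planned patient listing of PFS times and censoring reasons lets a reader find the cases. All of this stands and limits the severity.
- **Off-drug patients.** Those who stop treatment without progression are scanned quarterly until 12 months after first dose (Protocol 5.6.12 and 5.7.1). Neither the counts above nor the corrected cut-points deal with that schedule.

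**Conclusion.** The point holds. The three limits are correct, but the brackets that select them are not. For a last scan on days 106-119 or 162-175, the rule censors events after a single missed scan, contrary to the SAP's own censoring table. This follows from the SAP's schedule and window alone.

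The effect on the estimates rests on the assumed missed-scan rate and PFS distribution. Over the range tried with medians of 4-11 months, the 12-month rate is overstated by 0.5-3.7 points and the 6-month rate understated by 0.1-1.8. Medians and quartiles may shift too, but no figure is given because the simulated shift in the median was unstable between runs. In a small descriptive phase I study this is a modest error that should be corrected because it is plain and cheap to correct.

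Whether DoR is affected is unclear. The SAP applies the PFS censoring rules to responders without progression or death, which on its face leaves out rows 2 and 4.

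**What to change.** Move both cut-points to the early window edges:

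- last evaluable scan before day 106 (7 × 16 − 7 + 1): 126 days;
- days 106-161: 154 days;
- day 162 (7 × 24 − 7 + 1) onward: 182 days.

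Each limit then reaches exactly from the earliest last scan to the close of the second window: 176 − 50 = 126, 260 − 106 = 154, 344 − 162 = 182. Correct the printed derivation and the week labels in all three bullets; this also removes the double assignment of day 176. Say in the DoR section whether rows 2 and 4 apply and, if they do, use the same cut-points.

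The one drawback is that a few deaths or unscheduled progressions 1-13 days after two closed windows (days 261-273 or 345-357) would now count as events. The SAP's limits already leave up to 14 days of such slack after Weeks 8, 36 and 48, and in the simulations deaths of this kind were at most 0.4% of the events restored.

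The cost is two values in the SAP, the matching code and one sentence on DoR, with no new data. The SAP's introduction allows revision before final database lock; after lock, the correction should be documented in the clinical study report.
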